## 9.0 Vulnerable Populations

9.1 *Vulnerable Populations:* By nature of the disease and the fact COVID-19 is a rapidly evolving pandemic, with uncertain clinical course but potentially significant morbidity and mortality, all participants enrolled in this study are considered to be vulnerable. Some participants have additional characteristics that add to this vulnerability. Our criteria for inclusion and exclusion of each of these groups is summarized below, followed by our rationale and additional safeguards built into our study design. Our group has significant experience enrolling vulnerable patients in emergency care trials, and experience with a diverse population of potential participants in high stress situations.

## MEDICAL PROTOCOL (HRP-590)

SHORT PROTOCOL TITLE: Randomized control trial of losartan for inpatients with COVID-19

VERSION DATE:22APR2020

Population / Group	Identify whether any of the following populations will be targeted, included (not necessarily targeted) or excluded from participation in the study.
Children	Excluded from Participation
Pregnant women/fetuses/neonates	Excluded from Participation
Prisoners	Excluded from Participation
Adults lacking capacity to consent and/or adults with diminished capacity to consent, including, but not limited to, those with acute medical conditions, psychiatric disorders, neurologic disorders, developmental disorders, and behavioral disorders	Included/Allowed to Participate
Non-English speakers	Included/Allowed to Participate
Those unable to read (illiterate)	Included/Allowed to Participate
Employees of the researcher	Included/Allowed to Participate
Students of the researcher	Included/Allowed to Participate
Undervalued or disenfranchised social group	Included/Allowed to Participate
Active members of the military (service members), DoD personnel (including civilian employees)	Included/Allowed to Participate
Individual or group that is approached for participation in research during a stressful situation such as emergency room setting, childbirth (labor), etc.	Included/Allowed to Participate
Individual or group that is disadvantaged in the distribution of social goods and services such as income, housing, or healthcare.	Included/Allowed to Participate
Individual or group with a serious health condition for which there are no satisfactory standard treatments.	Included/Allowed to Participate
Individual or group with a fear of negative consequences for not participating in the research (e.g. institutionalization, deportation, disclosure of stigmatizing behavior).	Included/Allowed to Participate

Any other circumstance/dynamic that could increase vulnerability to coercion or exploitation that might influence consent to research or decision to continue in research.	Excluded from Participation
--	-----------------------------

#### 9.2 Additional safeguards:

- *Non-English speakers*: Excluding this group would compromise the principle of justice in clinical research. For groups likely to be enrolled given our known demographics (Spanish-speaking and Somali-speaking), we will translate informed consent forms (ICF) and use professional interpreters during both the consent and follow-up periods. These interpreters are available to our group during daytime hours by telephone. *We will request the use of the Short Form Consent for non-English speaking participants, and adhere to the regulations surrounding its use. When the translated ICsF become available, they will be used for non-English speakers.*
- *Employees or students of the researcher*: To minimize the potential for coercion, any employee or student of the research will undergo screening and informed consent by study personnel, but not by the investigator who is the direct supervisor of the vulnerable participant. The screening will not be performed by the study physicians or investigators, so this group may opt out in a deidentified fashion at that stage. Furthermore, if the potential participant wants to enroll, all interactions will occur with a different study investigator (such as the other co-principal investigator. These two clinical investigators work in different departments with different staff).
- *Undervalued or disenfranchised social group*: We will assure confidentiality, that they have the right to withdraw at any time without penalty, and they have the freedom to refuse to answer questions.
- *Active members of the military (service members), DoD personnel (including civilian employees)*: The status of participants of this group is not asked during the study nor known by study staff, and therefore vulnerability is not increased for anyone in this group.
- *Individual or group that is disadvantaged in the distribution of social goods and services such as income, housing, or healthcare*: We will assure participants that participation in this study will be treated with the strictest confidentiality, that they have the right to withdraw at any time without penalty, and they have the freedom to refuse to answer questions.
- *Individual or group with a serious health condition for which there are no satisfactory standard treatments*: We will assure that information from participants in this study will be treated with the strictest confidentiality, that participants have the right to withdraw at any time without penalty, and they have the freedom to refuse to answer questions.
- *Individual or group with a fear of negative consequences for not participating in the research (e.g. institutionalization, deportation, disclosure of stigmatizing behavior)*: The status of participants from these groups is not asked during the study nor known by study staff, and that vulnerability is not increased for anyone in this group.

## 10.0 Local Number of participants

*10.1 Locations:* Enrollment will occur on the ED (or designated COVID19 areas) of participating study sites see section 22.1).

*10.2 Number of participants:* We expect to enroll a minimum of 200 participants, with up to 220 participants when considering screen failures and withdrawals.

## **11.0 Local Recruitment Methods**

*11.1 Recruitment Process:* See section 5.0

*11.2 Identification of Potential Participants:* See section 5.0

*11.3 Recruitment materials:* N/A

*1.5 Payment:* Patients will be eligible for a \$25 gift card for their time to return for the 15-day blood draw for renal function testing if allowed by local site.

## **12.0 Withdrawal of Participants**

*12.1 Withdrawal Circumstances:* Participants may be withdrawn from research without their consent if they develop SAEs that the investigator believes to be likely related to the study drug. Participants may also withdraw from the study at any time for any reason. All patients withdrawn from the study will be analyzed using intent to treat principles.

*12.2 Withdrawal Procedures:* If patients choose to withdraw, study procedures including intervention and follow-ups will stop. Given the risks of transmission of infectious disease, written notification is not required. If the patient chooses to withdraw, the study team will ask if the patient is willing to allow continued electronic medical record evaluation for the determination of study endpoints (partial withdrawal). We will also ask if the patient wishes to withdraw consent for the use of future biologic specimens. If the patient declines to participate in any component of research, no further study data will be collected, biologic samples will be destroyed, but existing study data may be used. Each of these will be documented and stored as a study document.

*12.3 Termination Procedures:* Upon trial termination, study outcomes will be followed until completion. Case report forms and collection templates will be maintained in paper format (when application) and electronically for 7 years in accordance with regulations. Collected data will be used for secondary analyses with approval of the principal investigators in a deidentified fashion. Data entry will be completed, checked for accuracy, and locked for analysis within 1 year of enrollment of the final patient.

## **13.0 Risks to Participants**

*13.1 Foreseeable Risks:* Potential risks of losartan are detailed in consent forms. The most severe risks of losartan use include teratogenicity in the setting of pregnancy, hypersensitivity including angioedema, symptomatic hypotension, worsening of renal function, and electrolyte abnormalities. The most common side effects of losartan include fatigue, weakness, diarrhea, chest pain and anemia. Subjects will be rigorously screened to ensure that they are at low risk for complications due to losartan and they will be monitored closely for side effects and signs of toxicity. The package insert for Losartan has been included with this protocol. Clinical trial and post-marketing surveillance data (see package insert) demonstrate an

excellent safety profile. In over 4,000 patients, there was a low incidence of adverse events (2.3%) comparable to placebo (3.7%). The effects more common in losartan than placebo were clinically minor, including dizziness (3% vs 2%), upper respiratory infection (8% vs 7%), nasal congestion (2% vs 1%) and back pain (2% vs 1%). While losartan has the potential to cause symptomatic hypotension, four studies have identified losartan has a negligible effect on resting blood pressure and heart rate in healthy volunteers. While there may be a higher risk in critically ill patients, we will exclude patients with bedside clinician assessment of volume depletion that might increase the risk of side effects. It has been theorized there may be an increase risk of cardiac dysfunction in patients taking an ACE-I or ARB in COVID-19, though evidence for this effect is lacking. We will monitor troponin and BNP/pro-BNP levels in participants and report these data to the DSMB if measured clinically. In fact, the most recent preprinted (non-peer reviewed) data from China now suggest a protective effect based on retrospective data compared to other antihypertensive regimens. Nevertheless, based on this recent suggestion, we will track troponin and BNP/proBNP measurements in addition to our previously planned assessments of new episodes of hypotension and shock, and report these data to the DSMB. In addition, all patients are closely monitored for clinical purposes given their severity of illness, combined with daily assessments for AEs and SAEs will allow for early detection of side effects and reduce the risks to patients.

- 13.2 *Reproduction Risks:* Losartan is class D in pregnancy. Women of childbearing age will only be eligible for enrollment with a negative pregnancy test prior to enrollment. In addition, women breastfeeding will be excluded from the study.
- 13.3 *Risks to Others:* The primary risk to others is the risk to study personnel of becoming infected with COVID-19. To overcome this barrier, patients will be enrolled using an electronic consent process already established among our group for other studies. In addition, follow-up evaluations will preferentially be performed by telemedicine evaluation or phone evaluation. If a face-to-face evaluation or physical examination is required due to concern for adverse events, investigators trained and fitted with N95 masks or equivalent will perform a face-to-face examination. Participants will generate potential biohazards (oropharyngeal swabs), the safety steps surrounding which are discussed in section 6.2.

## 14.0 Potential Benefits to Participants

- 14.1 *Potential Benefits:* If randomized to the intervention arm, and if losartan is demonstrated to prevent the progression of acute lung injury, patients may benefit by having reduced lung injury, decreased need for oxygen or mechanical ventilation, or possibly lower mortality. If randomized to the control arm, there is no direct potential benefit to the patient. However, the proposed research has the potential to significantly benefit people infected with COVID-19.

[figure not shown]
## 15.0 Statistical Considerations

- 15.1 *Data Analysis Plan:* All analysis will focus on comparisons between the treatment and control groups. Demographics and other baseline clinical characteristics will be summarized using descriptive statistics. Descriptive statistics will be presented by treatment group using mean, standard deviation, median, and interquartile range (IQR) for continuous variables and frequencies and percentages for categorical

variables. The primary outcome, change in estimated P/F ratio at 7 days, will be summarized by group using the sample mean with 95% asymptotic confidence intervals. Patients discharged home will be given a pulse oximeter and called for the value at 7 days, adjusted for home O2 use as applicable. Patients who died will be penalized with a P/F of 0 (lower values indicate higher degree of respiratory failure) in order to address competing risks. Like respiratory SOFA, an adjustment is applied based on the use of PEEP. For the primary statistical analysis, Treatment groups will be compared using the two-sample t-test for unequal variances and the treatment effect will be summarized by the mean difference between groups. As a secondary statistical approach, we will also jointly model the longitudinal and time to event outcome under the assumption of informative missingness, jointly modeling P/F ratio measured daily and time to death using a shared random effects model. Finally, we will analyze these data on an ordinal scale (the respiratory SOFA score), which is a 0-4 ordinal scale derived from the estimated P/F ratio. In addition, patients who die prior to the day 7 assessment will be assigned a 5 for this analysis.

Secondary endpoints will be summarized by the sample mean or sample proportion, as appropriate, and compared using the unequal variance two-sample t-test or Chi-square test, as appropriate. Appropriate data transformations will be used to assure that assumptions of all statistical tests are met. Time-to-event endpoints will be summarized by Kaplan-Meier curves and compared using Cox proportional hazards regression. For all endpoints, we will complete secondary analyses comparing for important baseline variables that are unequally distributed between treatment groups. Preplanned subgroup analyses are planned by age (dichotomized at 50 and by decade), history of hypertension, sex, and smoking history, timing of randomization from symptom onset, and respiratory support needed at the time of randomization.

15.2 *Power Analysis:* Assuming a fixed sample size, we analyzed power using a number of assumptions. In general, studies with a similar degree of acute lung injury that we expect in this study have a standard deviation of estimated P/F ratio of 100-125. ARDS trials tend to have smaller SD due to narrowed inclusion criteria, while a single study of H1N1 with a lower severity of illness had a SD of 150. We calculated power for a variety of assumptions. If the SD is 125 or less, we will have >0.8 power to detect a difference in P/F of 50. Differences of less than this are of uncertain clinical significance. This method and outcome has more power than our alternative approach of respiratory SOFA, which is a more crude measure of the estimated P/F ratio.

15.3 **Data Integrity:** The principal investigator will manage oversight of quality control for collected data. Recruitment of subjects will be performed using inclusion/exclusion criteria defined above. Study data will be recorded within a RedCAP database, which is HIPAA compliant, password protected with variable assignable security access and an audit trail consistent with all regulatory requirements for maintenance of clinical trial data. Data summaries and quality control checks will be run routinely.

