**3.2 Secondary Endpoint(s)/Event(s)/Outcome(s):**

**3.3** There will be 7 secondary endpoints:

- To ensure losartan is safe and well tolerated in hospitalized patients with COVID-19, we will:
  - Compare daily hypotensive episodes (MAP < 65 mmHg) prompting intervention (indicated by a fluid bolus  $\geq 500$  mL)
  - Hypotensive episodes requiring intervention (vasopressors or fluid bolus)
  - Determine the incidence of new or worsening renal failure

- Daily Sequential Organ Failure Assessment (SOFA) score to day 10. If data are unavailable for any given organ failure, we will use the last value carried forward approach.
- Change in estimated P/F ratio daily between groups
- In-hospital, 28, and 90-day mortality (by using state death certificate or social security death index data)
- Resource utilization as assessed by: ICU admission, ventilator free days, oxygen free days, vasopressor free days, ICU and hospital length of stay
- Respiratory failure as measured by the utilization of Bilevel Positive Airway Pressure (BiPAP), high flow nasal cannula, mechanical ventilation or extracorporeal membranous oxygenation (ECMO) utilization, as well as trends in S/F ratio.
- Symptomatic improvement as assessed by the dyspnea PROMIS and SF-12 assessments of dyspnea and functional status
- Percentage of subjects reporting each severity rating on the *7-point ordinal scale* [ Time Frame: Day 15 ]
  - The *7-point ordinal scale* is an assessment of the clinical status at the first assessment of a given study day. The scale is as follows: 1) Death; 2) Hospitalized, on invasive mechanical ventilation or extracorporeal membrane oxygenation (ECMO); 3) Hospitalized, on non-invasive ventilation or high flow oxygen devices; 4) Hospitalized, requiring supplemental oxygen; 5) Hospitalized, not requiring supplemental oxygen; 6) Not hospitalized, limitation on activities; 7) Not hospitalized, no limitations on activities.
  - Change in viral load (nasopharyngeal or oropharyngeal swab and blood)

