1.4 *Justification of the primary outcome:* This trial seeks to mitigate lung injury from Covid-19 rather than treating the viral infection. Most patients present to the hospital secondary to dyspnea and pneumonia, and the primary mechanism of death is via respiratory failure progressing to multi-system organ failure. Prevention of progression of acute lung injury with an angiotensin receptor blocker such as losartan may decrease estimated P/F ratio, a validated measure of lung dysfunction that accounts for differences in the level of ventilatory support. We considered respiratory SOFA score, but this crude ordinal measurement is estimated off of the estimated P/F ratio, which will provide a more precise measurement of the same physiology. **Estimated P/F is a clinically relevant outcome not only to patients, but also to the healthcare system due to overwhelming surge of patients straining hospital resources** which not only puts patients with COVID-19 at risk, but also those admitted to the hospital for other reasons.

- *Rationale for the timing of the primary endpoint:* The average time from hospitalization to mechanical ventilatory support is 2-3 days, and average length of hospital stay is 10 days. We considered a 3 day outcome time point to minimize the need for home measurement and early death. However, >24 hours is required to reach steady state levels of drug, and 3 days is likely too early to detect a treatment benefit. We also considered 10 days, but this increases competing risks and decreases the sensitivity and strength of using the continuous primary outcome but increasing the proportion of patients who either die or recover, skewing the data. We

believe 7 days to represent the optimal balance of these competing concerns.

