**3.4 Justification of the secondary outcomes:** Patients severely infected with respiratory dysfunction may be at increased risk of volume depletion, acute kidney injury, or the development of hypotension, so we will systematically track these measured instead of relying upon adverse event reporting which introduces the potential for bias. We will measure P/F ratios daily in case our choice of 7 days proves incorrect. SOFA score is a validated measuring of organ failure in critically ill populations that can be determined. Death is clinically important, but we do not believe our sample size is adequately powered to detect a difference in this outcome. Resource utilization and respiratory support are critical in surge capacity situations and of relevance to this disease process. Validated study instruments to assess dyspnea and physical function will assess patient-centered outcomes and strengthen the biologic plausibility of the intervention. The 7-point ordinal scale described is used by other ongoing Covid-19 clinical trials and will allow harmonization of the trial results. Changes in viral load are important to assess the theoretical possibility of losartan induced ACE2 expression leading to increased viral entry, propagation, and shedding.

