## 4.0 Study Interventions / Interventional Agents

**4.1 Intervention arm:** The intervention is losartan, an angiotensin receptor blocker prepared in suspension per the package insert, administered at 50 mg PO twice daily for 10 days (patients with eGFR 30-59 mL/min/1.73 m^2 will be given 50 mg once daily) or until hospital discharge, whichever comes first. The supply of suspension is stable for 4 weeks refrigerated according to the package insert. Any unused doses will be discarded if unused by the 28 day time point.

- **Rationale for the duration of the intervention:** The average duration of mechanical ventilation caused by Covid-19 is approximately 14 days. We expect that if a benefit is observed, it will become apparent in that time frame. We have chosen to stop treatment at the time of discharge as the participant will have already demonstrated significant clinical improvement, and would introduce significant logistical limitations.
- **Rationale for the dose of treatment:** The lowest dose of losartan is 25 mg orally. The maximum clinical dose is 100 mg daily. Losartan has a half-life of 2 hours with an active metabolite E3174 of 6-9 hours. The threshold for blockade of angiotensin-II receptor is at least 20 mg per day. Twice daily dosing has been shown to potentiate angiotensin-II receptor blockade compared with once daily dosing. At this dose, extrapolated data suggests <70% inhibition of angiotensin-II receptors. At the highest maximum allowable dose (50 mg twice daily) we would anticipate >80% inhibition of angiotensin-II receptor. We believe this is necessary as these patients have significant pro inflammatory response. Recent reports indicate that patients with COVID19 have increased plasma Ang II levels and that Ang II levels correlate with COVID19 disease severity and viral load. AT1R inhibition is associated with decreased activity of STAT1 and NFkB downstream signaling as confirmed by western blot analysis. Furthermore, since our initial submission Losartan has been identified for its potential inhibitory effects on SARS-CoV2 viral life cycle based on

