[Patient Safety] A recommendation to suspend, alter the study, or stop for harm would occur if during continuous monitoring there is strong evidence that the rate of IRB-reported SAEs was significantly higher in the experimental group than in the placebo group. SAEs (including increasingly level of ventilator support and initiation of vasopressors, the two SAEs of interest) will be reported within 24 hours, allowing for continuous study monitoring. For the inpatient cohort, we propose formal interim analyses for safety at 10%, 20%, and 30% of enrollment. A 50% preplanned interim analysis for safety, efficacy, and futility is planned with specific stopping rules provided to the DSMB as a guide. Assuming a baseline mortality rate of 10%, this corresponds to formal hypothesis testing after every ~2 events initially, and decreasing as data accumulate. Despite the lower number of formal preplanned analyses, the DSMB will still receive near *real-time reporting of deaths*, and can deviate from this strategy and perform earlier testing if desired.

They retain authority to change this plan if the continuous reporting suggests harm prior to the first formal planned assessment if they feel that a formal hypothesis test is warranted. In addition, the DSMB may request additional safety assessments after the 50% assessment, if they feel that additional formal testing is needed.

[Efficacy] – A preplanned interim analysis at 50% of enrollments will assess for early efficacy or futility.

The DSMB will operate in accordance with guidelines established by the FDA in “Guidance for Clinical Trial Sponsors: Establishment and Operation of Clinical Trial Data Monitoring Committee” jointly published by the CBER, CDER and CDRH of the FDA (<https://www.fda.gov/regulatory-information/search-fda-guidance-documents/establishment-and-operation-clinical-trial-data-monitoring-committees>) . The key elements include:

1. Expertise and independence: The members must have expertise in the area of study, not be study authors and have no financial conflict of interest.
2. Members will sign a confidentiality agreement.
3. It is preferred that the DSMB have a face-to-face initial meeting, but can meet by telephone thereafter more frequently.
4. All meetings must follow standard operating procedures (SOPs).

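### No ordinal method is named for the day-15 seven-point scale, and the likelier test ignores category order; free-days and length of stay also lack a death rule

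*Combined protocol and SAP*

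**What the plan says.** - **Test rule.** Section 15.1 gives one rule for all secondary endpoints: summarise by mean or proportion, then they are "compared using the unequal variance two-sample t-test or Chi-square test, as appropriate". Kaplan-Meier and Cox methods are reserved for time-to-event endpoints, which are not listed.
- **Seven-point scale.** Section 3.3 gives the day-15 endpoint as "Percentage of subjects reporting each severity rating on the" scale, with death as category 1 and unrestricted activity at home as category 7. Section 3.4 includes it because it is used in other COVID-19 trials and "will allow harmonization of the trial results".
- **Resource use.** Section 3.3 lists "ventilator free days, oxygen free days, vasopressor free days, ICU and hospital length of stay" by name only. No window is given for the free-days, and no death rule for any of these endpoints. Section 3.4 says: "Resource utilization and respiratory support are critical in surge capacity situations".
- **Death rules that do exist.** Section 15.1 scores death as P/F = 0 for the primary endpoint and as 5 in its respiratory SOFA version. Neither rule is extended to free-days or stay.

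**The concern.** A Chi-square on a 2 x 7 table gives the same p-value however the columns are arranged, so it cannot tell a shift towards recovery from a reshuffling of categories. It also yields no estimate. If the effect is a steady move along the scale, power is lost, and the trial reports no single effect size of its own for an endpoint chosen so that its results can be set beside others.

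Free-days without a death rule are not fully defined. A patient who dies after a few ventilated days may score zero, or nearly the whole window, or be left out. When mortality differs by arm these choices give different answers from the same data. Length of stay has a milder form of the problem: an early death shortens it and a late death can lengthen it.

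**Working it through.** **Inputs from the documents.** 200 patients (sections 10.2, 23.1), 1:1 (section 4.6), so 100 per arm; 10% baseline mortality (section 18.3); ventilation of about 14 days (section 4.1); mean stay of 10 days (rationale for the timing of the primary endpoint). **Assumed:** two-sided 5% level, category distributions, odds ratios, comparison mortalities, share of survivors ventilated.

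**The plan's own figure.** The only stated power is for the primary endpoint: above 0.8 for a difference of 50 with SD 125. z = 50 / (125 x sqrt(2/100)) = 2.83; 2.83 - 1.96 = 0.87; power 0.81. It reproduces. No power is claimed for the endpoints discussed here.

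**Order.** Take counts 14/16/10/14/10/20/16 v 7/10/7/12/11/26/27. Chi-square gives p = 0.235 both as listed and after the categories are permuted. The rank test goes from p = 0.005 to p = 0.85.

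**Chi-square power by formula.** Control, death to full recovery (%): 10/10/6/10/8/26/30. Halving each cumulative odds (odds ratio 2.0) gives 5.3/5.8/3.8/7.0/6.2/25.6/46.2. The noncentrality is n x sum of (p - q)^2 / (p + q), which is 100 x 0.072 = 7.2. Power of 80% on 6 df needs 13.62, so 13.62 / 0.072 = 189 per arm. A 1-df test needs a noncentrality of only 7.85, and the corresponding rank-test figure is 109.

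**Simulation, 100 per arm, proportional odds true:**

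| Control (%) | OR | Chi-square | Rank | Prop. odds | Welch on 1-7 |
|---|---|---|---|---|---|
| 10/10/6/10/8/26/30 | 2.0 | 0.48 | 0.77 | 0.79 | 0.72 |
| 15/20/10/15/5/20/15 | 2.0 | 0.50 | 0.79 | 0.80 | 0.78 |
| 5/5/5/10/5/30/40 | 2.0 | 0.44 | 0.74 | 0.76 | 0.65 |
| all three | 1.75 | 0.29-0.33 | 0.57-0.61 | not run | 0.49-0.61 |
| all three | 1.5 | 0.15-0.19 | 0.33-0.38 | not run | not tabulated |

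A second set of three control distributions, each with 10% deaths, gave 0.43-0.50 (Chi-square) and 0.73-0.80 (rank) at OR 2.0. With no effect, Chi-square, rank and Welch reject in 4-6% of trials, and the fitted proportional-odds test in 4.9-6.1% (1,500 fits per cell).

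**When the effect is not a consistent shift** (first control; power to within about 0.01):

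| Pattern | Chi-square | Rank | Welch |
|---|---|---|---|
| Only death and ventilation halved | 0.26 | 0.25 | 0.35 |
| Only a 12-point move from category 6 to 7 | 0.38 | 0.14 | 0.07 |
| More deaths but more full recoveries | 0.45 | 0.05 | 0.11 |

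**Ventilator-free days.** Assume a 28-day window, with 20% of survivors ventilated for 14 days in both arms. Survivor mean = 0.8 x 28 + 0.2 x 14 = 25.2. With deaths excluded the arms do not differ. With death = 0 the difference is the mortality gap x 25.2:
- 10% v 12%: 0.02 x 25.2 = 0.5 days
- 10% v 15%: 0.05 x 25.2 = 1.3 days
- 10% v 20%: 0.10 x 25.2 = 2.5 days

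The sign can also change. Suppose control has 10 deaths and 20 ventilated survivors, and losartan 5 and 25. With death = 0: (70 x 28 + 25 x 14)/100 - (70 x 28 + 20 x 14)/100 = 23.1 - 22.4 = +0.70. With deaths excluded: 2310/95 - 2240/90 = -0.57. With death = 0, the window alone moves the difference from 0.00 (10 days) to +3.80 (90 days). With equal mortality (10 deaths each; 20 v 15 ventilated survivors) the death rules give 0.70-0.78.

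**Stay.** Let survivors stay 10 days in both arms and deaths occur on day d. Counting days up to death at 10% v 20% mortality, the difference is 0.1 x d - 1: -0.6 at day 4, 0 at day 10, +0.6 at day 16. It reaches significance in 7-14% of trials.

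**The case against.** - **Chi-square is not prescribed.** Correct. Section 15.1 would also permit a Welch test on scores 1-7, which uses order. A reader might infer that the plan commits to Chi-square; it only makes that the likelier reading.
- **Harmonization survives.** A reader might infer that the scale cannot be pooled with other trials. The documents do not support that: the percentages in every category, with the arm sizes, allow anyone to compute a common odds ratio. What is missing is the trial's own prespecified estimate and test.
- **An ordinal model is not always better.** This stands. If only death and ventilation improve, the pattern closest to the trial's aim, Welch beats the rank test on all three controls (0.35 v 0.25, 0.61 v 0.59, 0.16 v 0.10) and Chi-square is about level with the rank test (0.26, 0.52, 0.11). The firm request is for one named order-using test; proportional odds is a preference.
- **Power is modest anyway.** At odds ratio 1.5 no test is adequately powered with 100 per arm. True, and the plan claims no power here, but an ordinal test still has about twice the power of Chi-square under a consistent shift.
- **Choice after seeing the data.** A reader might infer that the free-day rules will be chosen with results in view. Nothing says so. Everyone except the drug service is blinded (section 4.6), so the rules can still be fixed first. The supportable statement is that they could otherwise be chosen late.

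**Conclusion.** The point holds as an inexpensive improvement to secondary analyses. For the seven-point scale, naming an order-using method raises power from about 0.44-0.51 to 0.74-0.80 at odds ratio 2.0, and from 0.15-0.19 to 0.33-0.38 at 1.5, provided the effect is a consistent shift; the category distributions are assumed. Under other patterns there is little gain, or a loss.

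The missing window and death rules are mainly missing detail. They matter in practice when mortality differs by arm, and the size follows the gap: 0.5, 1.3 or 2.5 days for ventilator-free days at assumed comparison mortalities of 12%, 15% and 20%. Quoting 2.5 days as the general effect would overstate it, because that figure needs mortality to double. The effect on stay is small. A reader might extend the criticism to the primary endpoint; its test and death rule are stated in section 15.1, and it is unaffected.

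**What to change.** **Scale.** In section 15.1, name one order-using comparison for the day-15 scale, preferably a proportional-odds model reporting a common odds ratio with its 95% confidence interval. Keep the category percentages as description, so that a pattern that is not a consistent shift remains visible. This is a wording change. Its downside is the low power under non-uniform effects shown above.

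**Free-days and stay.** Before unblinding, state one window and one death rule for ventilator-, oxygen- and vasopressor-free days, for example 28 days with death = 0. State also how in-hospital death is handled for ICU and hospital stay, and whether stay is analysed as time-to-event. Another window would do if it is stated. No new endpoints are needed.

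**Cost.** Death and discharge dates, ventilatory support and daily vasopressors are already collected (section 1.6). Scheduled daily evaluation covers 10 days plus day 15 (section 5.4), so a 28-day window needs record review after day 15 for ventilator and vasopressor days, and a home-oxygen stop date asked for at the day-28 contact. Section 1.5 already provides for record review. With death = 0, free-days partly measure mortality, so they should be read beside it.
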